8.5.5 Pharmacokinetics

Pharmacokinetic (PK) samples will be collected at the visits defined in the assessment schedule (Table 8-1) and Table 8-3.

All blood samples will be drawn by direct venipuncture in a forearm vein.

The actual sample collection date and exact time will be entered on the PK blood collection summary eCRF. The reason for not taking blood samples will be captured in the eCRF.

The bioanalyst will receive a copy of the randomization schedule to facilitate analysis of the PK samples. The bioanalyst will provide the samples' concentration data to the team under blinded conditions. Bioanalyst will keep this information blinded until the interim clinical database lock.

PK sample handling, labeling and shipment instructions:

Laboratory manuals will be provided by the central laboratory with detailed information on sample collection, sample handling and shipment.

Tubes and labels will be provided by the central laboratory with study/sample type information pre-printed on the label.

Table 8-6 PK sample log

Week	Timepoint	PK sample number*	PK collection number
BSL	0 h (pre-dose)	1	1
BSL	0.5 h	2	1
Week 4	0 h (pre-dose)	3	2
Week 4	0.5 h	4	2
Week 8	0 h (pre-dose)	5	3
Week 8	0.5	6	3
Week 16	0 h (pre-dose)	7	4
Week 24	0 h (pre-dose)	8	5
Week 24	0.5 h	9	5
Week 25	anytime	10**	5
Week 48	0 h (pre-dose)	11	6
Week 48	0.5 h	12	6
Week 52	anytime	13**	6
Week 60	anytime	14**	6

[figure not shown]
* If a PK sample is collected at an unschedule visit, the sample number will follow the pattern: 1001, 1002, etc.

[figure not shown]
** Post-dose time point for sample number 10 refers to the dose given at Week 24. Post-dose time points for sample numbers 13 and 14 refer to the last dose given at Week 48.

PK analytical methods

An ELISA method will be used for the bioanalytical analysis of AIN457 in serum, with an anticipated lower limit of quantification (LLOQ) of 80 ng/mL. The detailed method description to assess the Secukinumab concentration will be described in the Bioanalytical Data Report (BDR).

Concentrations below the LLOQ will be reported as “zero” and missing data will be labeled as such in the BDR.

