Subjects who discontinue study treatment or who decide they do not wish to participate in the study further should NOT be considered withdrawn from the study UNLESS they withdraw their consent (see 'Withdrawal of Informed Consent' [Section 9.1.2](#)). **Where possible, they should return for the assessments indicated** in the Assessment Schedule. If they fail to return for these assessments for unknown reasons, every effort (e.g. telephone, e-mail, letter) should be made to contact the subject/pre-designated contact as specified in the lost to follow-up [Section 9.1.3](#). This contact should preferably be done according to the study visit schedule.

If the subject cannot or is unwilling to attend any visit(s), the site staff should maintain regular telephone contact with the subject, or with a person pre-designated by the subject. This telephone contact should preferably be done according to the study visit schedule.

Subjects who prematurely discontinue or withdraw during a specific treatment period should return, 4 weeks after the last study treatment, for the final visit within that treatment period (i.e., Week 16 for treatment period 1 or Week 52 for treatment period 2), as well as return for the follow-up visit (i.e., Week 60) 12 weeks after the last study treatment, see [Table 8-1](#). The final visit should be performed before any new treatment is initiated.

For subjects who are lost to follow-up (i.e. those subjects whose status is unclear because they fail to appear for study visits without stating an intention to withdraw), the investigator should show "due diligence" by documenting in the source documents steps taken to contact the subject, e.g. dates of telephone calls, registered letters, etc.

The investigator must also contact the IRT to register the subject's discontinuation from study treatment.

If discontinuation occurs because treatment code has been broken, please refer to Emergency breaking of treatment code [Section 6.6.3](#).

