9.2 Study completion and post-study treatment

A subject will be considered to have completed the study if he/she received a maximum of 52 weeks of study treatment and upon completion of the scheduled study assessments and procedures up to and including visit Week 60.

Information on the subject's completion or discontinuation of the study and the reason for discontinuation will be recorded on the appropriate Study Phase Completion eCRF page.

The investigator must provide follow-up medical care for all subjects who are prematurely withdrawn from the study, or must refer them for appropriate ongoing medical care. This medical care may include initiating another treatment outside of the study as deemed appropriate by the investigator. This treatment may be any non-biologic DMARD. In case of a biologic treatment, a waiting period of 3 months before initiating the treatment is recommended.

If, at study completion, the investigator determines that a patient could benefit from continued secukinimab treatment, the physician may request access from Novartis, at no cost to the patient, if not commercially available and accessible.

10 Safety monitoring and reporting

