12.5.3 Pharmacokinetics

All subjects with concentration data will be included in the PK data analysis.

[figure not shown]
Pharmacokinetic variables

The following PK parameter will be determined: C_{min,ss}. C_{min,ss} will be determined using Phoenix software. Individual serum concentrations in µg/mL will be listed. All concentrations below the limit of quantification or missing data will be labeled as such in the concentration data listings. Concentrations below the limit of quantification will be treated as zero in summary statistics for concentration data only.

During modeling of the PK of secukinumab, the broad principles outlined in the [FDA Guidance for Industry: Population Pharmacokinetics](#) will be followed.

Statistical methods for pharmacokinetic analyses

Summary statistics by visit/time will be provided for the above mentioned parameter and will include arithmetic and geometric means, SD, median, minimum and maximum. Individual concentrations will be listed by subject.

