2.2 Analysis sets

The following analysis sets will be used in this trial:

Randomized set: The randomized set will be defined as all subjects who were randomized. Unless otherwise specified, mis-randomized subjects (mis-randomized in IRT) will be excluded from the randomized set.

Mis-randomized subjects are defined as those subjects who were mistakenly randomized into the IRT prior to the site confirming all eligibility criteria had been met and to whom no study medication was given. Mis-randomized patients are treated as screen failures.

Full analysis set (FAS): The FAS will be comprised of all subjects from the randomized set to whom study treatment has been assigned. Following the intent-to-treat principle, subjects will be evaluated according to the treatment assigned to at randomization, but actual stratum, if stratified randomization is used.

Safety set: The safety set includes all subjects who took at least one dose of study treatment during the treatment period. Subjects will be evaluated according to treatment received.

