2.3 Patient disposition, demographics and other baseline characteristics

2.3.1 Patient disposition

The number of subjects screened will be presented. In addition, the reasons for screen failures will be provided. The number and percentage of subjects in the randomized set who completed the study periods and who discontinued the study prematurely (including the reason for discontinuation) will be presented at the end of each treatment period (Week 16 and Week 52) and follow-up period, if appropriate, for each treatment group and all subjects.

For each protocol deviation (PD), the number and percentage of subjects for whom the PD applies will be tabulated. Protocol deviations due to COVID-19 will be reported in separate categories.

Additional analysis due to COVID-19 might be provided, e.g., summary of participants missed visit and/or treatment due to COVID-19.

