2.9 Pharmacokinetic endpoints

During modeling of the PK of secukinumab, the broad principles outlined in the [FDA Guidance for Industry: Population Pharmacokinetics] will be followed.

All completed subjects with quantifiable pharmacokinetic (PK) measurements will be included in the PK data analysis. Serum concentrations will be expressed in mass per volume units. All concentrations below the limit of quantification as well as missing data will be labeled as such in the concentration data listings. PK concentrations will be summarized by visit and treatment group. In addition to mean, standard deviation (SD), coefficient of variation (CV), median and quartiles, the geometric mean and geometric coefficient of variation (CV), minimum and maximum, as well as n and n(log) will be presented. The formula for deriving the geometric mean and CV (%) is as follows:

- CV(%) = (SD/mean)*100,
- geometric mean=exp((sum of log transformed data) / number of non-missing data points after log transformation),
- geometric CV = sqrt(exp(variance of log-transformed data)-1)*100.

In addition, sample number, concentration, sample date, sample time and elapsed time from first dose (in days) will be listed by treatment sequence.

Values below lower limit of quantification/below detection limit will be imputed by 0.

Novartis	Confidential	Page 23 of 45
SAP		Study No. CAIN457P12301

Pharmacokinetic data of the study treatment will be analyzed with a populationpharmacokinetic mixed effects model. The analysis will be based on a pooled data set, including PK samples from previous studies. The modeling approach will be further detailed in a modeling plan. Results will be reported separately.

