Table 3-2	Summary of power for continuous endpoints			
Endpoint	Mean change	Mean change from baseline		Power
	Secukinumab(N = 200 AS + 50 nr- axSpA)	Placebo (N = 200 AS + 50 nr- axSpA)	standard deviation	
hsCRP ¹	-0.79	0.09	0.867	99%
BASDAI	-2.61	-1.48	2.241	99%
BASFI	-2.14	-1.13	2.253	99%
SF-36 PCS	6.87	3.99	6.898	99%
ASQoL	-4.46	-2.56	4.714	99%
PSQI ²	-1	0	3.9	81%

¹ hsCRP is in log scale

² Source: mean change from baseline is from Karatas et al 2018 (AS study, median was used) and common standard deviation is from Taylor-Gjevre et al 2011 (RA study, largest standard deviation was used).

4 Change to protocol specified analyses

No change from protocol specified analysis was made.

5 Appendix

5.1 **Description of efficacy variables**

Assessment of Spondyloarthritis International Society criteria (ASAS) response criteria

The ASAS response measures consist of the following assessment domains (Sieper 2009)

Main ASAS domains:

- 1. Patient's global assessment of disease activity measured on a VAS scale
- 2. Patient's assessment of back pain, represented by either total or nocturnal pain scores, both measured on a VAS scale. For ASAS response analyses, the total back pain will be used.
- 3. Function represented by BASFI average of 10 questions regarding ability to perform specific tasks as measured by VAS scale
- 4. Inflammation represented by mean duration and severity of morning stiffness, represented by the average of the last 2 questions on the 6-question BASDAI as measured by VAS scale (at least one question is needed)

Additional assessment domains:

2. C-reactive protein (acute phase reactant)

ASAS40

Novartis	Confidential	Page 29 of 45
SAP		Study No. CAIN457P12301

The ASAS40 response is defined as a $\ge 40\%$ improvement and an ≥ 2 units on a scale of 10 in at least three of the following 4 domains: back pain, patient global assessment of disease activity, physical function (BASFI) and inflammation (mean score of items 5 and 6 of the BASDAI) without any worsening in the remaining domain.

ASAS20

The ASAS20 response is defined as an improvement of $\ge 20\%$ and ≥ 1 unit on a scale of 10 in at least three of the four main domains and no worsening of $\ge 20\%$ and ≥ 1 unit on a scale of 10 in the remaining domain.

ASAS 5/6

The ASAS 5/6 improvement criteria is an improvement of $\geq 20\%$ in at least five domains.

ASAS partial remission

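### SAP 2.9 limits the PK analysis to completed subjects with quantifiable measurements, with completed undefined; protocol 12.5.3 includes everyone with concentration data, and SAP Section 4 declares no change

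*SAP*

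**What the plan says.** The two documents define the PK population differently.

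- Protocol 12.5.3: "All subjects with concentration data will be included in the PK data analysis". It sets no condition on completion or on quantifiability.
- SAP 2.9: "All completed subjects with quantifiable pharmacokinetic (PK) measurements will be included in the PK data analysis".
- SAP Section 1 undertakes to document deviations from the protocol. SAP Section 4 then states: "No change from protocol specified analysis was made".

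SAP 2.2, introduced by "The following analysis sets will be used in this trial", names a randomized set, a full analysis set and a safety set. It has no PK set that could settle the matter.

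Completion appears in three other places, none of which SAP 2.9 cites:

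- SAP 2.3.1 counts subjects "who completed the study periods and who discontinued the study prematurely", at Week 16, at Week 52 and, if appropriate, for follow-up.
- Protocol 9.2 ties completion of the study to a maximum of 52 weeks of treatment and "upon completion of the scheduled study assessments and procedures up to and including visit Week 60".
- The protocol glossary places study completion at the later of two events: a last evaluation visit or stopping study drug. A subject who stopped early can meet this.

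**The concern.** Neither the full analysis set nor the safety set carries a completion condition. SAP 2.9 imposes one on PK alone, so membership depends on something that happens after randomization. Two programmers could also build different sets from the same sentence, because it names no period, visit or definition.

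The protocol plans to keep observing subjects who stop treatment. Under 9.1.1, subjects who leave early "should return, 4 weeks after the last study treatment, for the final visit within that treatment period", and Section 8 asks all subjects for a follow-up visit. Protocol 6.5.3.1 requests a PK sample in potential liver-injury cases, where treatment may already have been stopped. Concentrations of this kind are collected but may not be summarized.

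Exposure also matters to this trial's argument. Protocol 4.2 and 6.5.1 justify the regimen by the exposure it is expected to give relative to the subcutaneous doses. The concentration summaries describe that exposure in these subjects, so their population should be clear.

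**Working it through.** The plan gives no figure to reproduce here. The check compares texts and adds a count to show scale.

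**Conditions for inclusion**

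| Condition | Protocol 12.5.3 | SAP 2.9 |
|---|---|---|
| Has concentration data | yes | yes |
| Has completed | not required | required, undefined |
| Has quantifiable measurements | not required | required |

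Both sentences are intact, so redaction does not explain the difference. SAP 2.9 and SAP Section 4 cannot both be right.

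**Inputs**

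- Group size 250 (protocol 12.8.1).
- Anticipated drop-out of 10% before Week 16 (protocol Section 5).
- PK samples 1 to 14 (protocol Table 8-6). Sample 1 precedes the first dose. Samples 2 to 6 run from baseline 0.5 h to Week 8 0.5 h. Sample 7 is Week 16 pre-dose, and samples 8 to 12 fall at Weeks 24, 25 and 48. Samples 13 and 14 are taken at Weeks 52 and 60: "Post-dose time points for sample numbers 13 and 14 refer to the last dose given at Week 48".
- Assumption: drop-out is equal between arms.

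**Subjects affected on a Week 16 or later reading**

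- 0.10 × 500 = 50 overall, or 0.10 × 250 = 25 in the secukinumab arm.
- The documents give no drop-out rate to Week 60. An assumed 15% to 25% would give 0.15 × 500 = 75 to 0.25 × 500 = 125 overall on the Week 60 reading.

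**Concentrations from those 25 subjects, same condition**

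- Lowest: only the baseline 0.5 h sample each, 25 × 1 = 25.
- All five samples 2 to 6 each: 25 × 5 = 125, out of 250 × 5 = 1,250 at those time points, or 10%.
- Highest: those five plus one at the final visit and one at follow-up, 25 × (5 + 2) = 175.

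**Post-first-dose samples excluded for one secukinumab-arm subject, by reading**

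| Subject | Period 1 (Week 16) | Week 52 | Week 60 | Glossary |
|---|---|---|---|---|
| Leaves after Week 8 sampling and before Week 16, no return visit | 5 (samples 2–6) | 5 | 5 | could be 0 |
| Leaves between the Week 16 and Week 24 samples, no return visit | 0 | 6 (samples 2–7) | 6 | could be 0 |
| Misses only Week 60 | 0 | 0 | 12 (samples 2–13) | could be 0 |

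A placebo subject who switched at Week 16 and missed only Week 60 would lose samples 8 to 13, which is 6, on the Week 60 reading and none on the Week 16 or Week 52 reading.

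**The case against.** Four points can fairly be made on the other side.

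- **The loss may be small.** Under the glossary, an early leaver who attends a final visit can count as having completed, and the protocol asks for that visit. The subjects behind the upper count of 175 are those who attend both return visits, so on that reading their loss could be zero. This stands: the counts above hold only if *completed* means completing Week 16 or later.
- **The context favors study completion.** This SAP serves the final analysis and does not repeat the Week 16 outputs, so completing Treatment Period 1 is the less natural meaning. That narrows the ambiguity. It does not choose between protocol 9.2 and the glossary, and it does not remove the mismatch with protocol 12.5.3.
- **The 10% is arithmetic by construction.** Removing 10% of subjects who each have a full set of samples removes 10% of the samples. That is correct, and it says nothing about whether any mean would move.
- **Little is lost.** SAP 5.3 says all collected data are listed, and no hypothesis test uses the PK summaries. Both are true and keep the point minor.

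A reader might infer that the word quantifiable discards every below-LLOQ value. The documents do not support that, since SAP 2.9 itself imputes such values as 0 and labels them in the listings. What stays open is whether a subject with only below-LLOQ values belongs to the set. Such subjects would probably be mainly placebo subjects who never switched, and protocol 6.4 lets the bioanalyst avoid analyzing placebo samples.

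**Conclusion.** The mismatch holds and rests on the wording alone: the SAP narrows the protocol's PK population, leaves the narrowing condition undefined, and declares no change. It is a minor point with a nearly free remedy.

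The size is not established. About 25 of 250 secukinumab-arm subjects is an illustration that needs the 10% drop-out to occur, equal drop-out between arms, and a Week 16 or later reading. On the glossary reading the loss could be near zero.

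Two further inferences are tempting:

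- **That the reported means are biased in a known direction.** The documents do not relate leaving the study to concentration, so neither size nor direction can be derived.
- **That only the descriptive concentration tables can be touched.** This is too firm. Protocol 12.5.3 prespecifies Cmin,ss, which would be affected if derived on this set. SAP 2.9 sends the population PK modeling approach to a separate plan but does not say whether that model follows the same inclusion rule.

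No efficacy or safety test is affected.

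**What to change.** Replace the inclusion sentence in SAP 2.9 with the protocol's own: "All subjects with concentration data will be included in the PK data analysis". Leave the SAP's below-LLOQ rule as it is. State that the set includes subjects whose only values are below the LLOQ, and say whether Cmin,ss and the population PK model use this set.

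If a completers-only table is wanted, make it supplementary. Define *completed* by naming the period or visit, say whether a subject who stops treatment but stays in follow-up counts, and record the restriction in SAP Section 4.

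The cost is a short edit to SAP 2.9 and a re-run of the PK summaries. No new data are needed.

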2.10 PD analyses

Novartis SAP	Confidential	Page 24 of 45 Study No. CAIN457P12301

Novartis	Confidential	Page 25 of 45
SAP		Study No. CAIN457P12301

2.11 Patient reported outcomes (PROs)

Patient reported outcomes will be evaluated based on FAS unless otherwise specified.

BASDAI

The following variables will be evaluated:

• BASDAI

For BASDAI, summary statistics of observed data by visit and change from baseline in BASDAI will be provided for each treatment.

BASFI

See Section 5.1 Description of efficacy variables for details.

Patient's global assessment of disease activity (VAS)

Summary statistics of observed data by visit and change from baseline in patient's global assessment of disease activity will be provided for each treatment.

Patient's assessment of back pain intensity (VAS)

Summary statistics of observed data by visit and change from baseline in patient's assessment of back pain intensity will be provided for each treatment.

SF-36

The following variables will be evaluated:

- SF-36 domain scores (based on a scale of 0-100)
- SF-36 PCS (norm-based scores)
- SF-36 PCS (improvement of ≥ 2.5 points, Lubeck 2004)

For the change from baseline in SF-36 summary scores (PCS), summary statistics will be provided using observed data for each treatment regimen.

For the responder analyses, the proportion of responders will be descriptively summarized along with its 95% CI for each randomized treatment based on observed data.

The SF-36 domain scores will be summarized by treatment.

ASQoL

Summary statistics of observed data by visit and change from baseline in ASQoL will be provided for each treatment.

Novartis SAP	Confidential	Page 26 of 45 Study No. CAIN457P12301

PSQI

Summary statistics of observed data by visit and change from baseline in PSQI score will be provided for each treatment.

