1.2 Purpose

The purpose of this global study is to demonstrate the efficacy, safety, and tolerability of an intravenous (i.v.) regimen of secukinumab compared to placebo in subjects with active axSpA, including AS and nr-axSpA at Week 16 despite current or previous NSAID, conventional DMARD and/or anti TNF therapy. In addition, to further support efficacy and safety of an i.v. regimen, data will be collected for up to 52 weeks of treatment. Efficacy and safety data may be used to support the registration of i.v. secukinumab in the US and other countries for treatment of subjects with active axSpA.

[figure not shown]
2 Objectives and endpoints

Table 2-1 Objectives and related endpoints

Objective(s)	Endpoint(s)
Primary objective(s)	Endpoint(s) for primary objective(s)

 To demonstrate that the efficacy of i.v. secukinumab at Week 16 is superior to placebo in subjects with active axSpA (AS and nr-axSpA) based on the proportion of subjects achieving an ASAS40 (Assessment of SpondyloArthritis International Society criteria) response. 	
 ASAS40 response at Week 16, defined as improvement of $\geq 40\%$ and an absolute improvement from baseline of ≥ 20 units (range 0–100) in ≥ 3 of the following 4 domains: back pain [10 cm visual analogue scale (VAS)], patient global assessment of disease activity (10 cm VAS), physical function (BASFI; range 0–100) and inflammation (mean score

[figure not shown]
Objective(s)	Endpoint(s)
	of items 5 and 6 of the BASDAI; both 10 cm VAS) without any worsening in the remaining domain.
Secondary objective(s)	Endpoint(s) for secondary objective(s)

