6.2.3 Rescue medication

Rescue medication is defined as any new therapeutic intervention or a significant change to ongoing therapy made because a subject is experiencing either no benefit from participation in the trial or worsening / exacerbation of his/her disease.

Rescue medication should not be used before completion of Week 16 assessments (see [Table 8-1](#)). Although no subject will be restricted from receiving necessary rescue medications for

lack of benefit or worsening of disease, if rescue with prohibited biologics (as described in [Section 6.2.2](#)) occurs prior to completion of Week 16 assessments, subjects will be discontinued from study treatment and enter into the follow-up period after an end of treatment visit. Efficacy will be assessed in detail at every study visit, and subjects who are deemed not to be benefiting from the study treatment based upon safety and efficacy assessments by the investigator or for any reason on their own accord will be free to discontinue participation in the study at any time.

Changes in concomitant therapy with NSAIDs are permitted after Week 16 assessments as per investigator's clinical judgment. After Week 16, the dose and regimen of other concomitant medications may be adjusted slowly at the investigator's discretion and recorded appropriately on the CRF page.

Any use of rescue medication must be recorded in the Prior/Concomitant medications eCRF.

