9.1 Discontinuation

9.1.1 Discontinuation of study treatment

Discontinuation of study treatment for a subject occurs when study treatment is stopped earlier than the protocol planned duration and can be initiated by either the subject or the investigator.

The investigator must discontinue study treatment for a given subject if, he/she believes that continuation would negatively impact the subject's well-being.

The following circumstances **require** study treatment discontinuation:

- Withdrawal of informed consent (WoC)
- Emergence of the following adverse events:
 - a. Any severe or serious adverse event that is not compatible with administration of study medication, including adverse events that require treatment with an unacceptable co-medication
 - b. Onset of lymphoproliferative disease or any malignancy except for treated basal cell carcinoma, treated actinic keratoses, treated in situ carcinoma of the cervix or non-invasive malignant colon polyps which are being or have been removed
 - c. Life-threatening infection
 - d. Severe hypersensitivity reaction or anaphylactic reaction
- Any laboratory abnormalities that in the judgment of the investigator are clinically significant and are deemed to place the subject at a safety risk for continuation in the study (A general guidance on clinically notable laboratory values is provided in [Section 16.1](#).)
- Pregnancy
- Use of any biologic immunomodulating agent except secukinumab
- Any protocol deviation that results in a significant risk to the subject's safety

In addition to these requirements for study treatment discontinuation, the investigator should discontinue study treatment for a given subject if there is a lack of improvement or worsening of their symptoms, or if on balance, he/she thinks that continuation would be detrimental to the subject's well-being.

If discontinuation of study treatment occurs, the investigator should make a reasonable effort to understand the primary reason for the subject's premature discontinuation of study treatment and record this information.

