12.4.3 Handling of missing values/censoring/discontinuations

Missing data for ASAS40 response and other binary efficacy variables (e.g., ASAS 5/6, etc.) for data up to Week 16 will be handled as follows:

1. Patients who drop out of the trial for any reason will be considered as non-responders from the time they drop out through Week 16
2. Patients who do not have the required data to compute responses (e.g., ASAS components) at baseline and at the specific timepoint will be classified as non-responders at the specific timepoint.

Patients who are unblinded prior to the scheduled time point will be considered non-responders from the time of unblinding up to Week 16. The primary analysis will use the non-responder imputation.

Continuous variables (e.g., ASAS components) will be analyzed using a mixed-effects model repeated measures (MMRM) which is valid under the missing at random (MAR) assumption. As such, single-point imputation of missing data will not be performed (e.g., LOCF). For analyses of these parameters, if all post-baseline values are missing then these missing values will not be imputed and this patient will be removed from the analysis of the corresponding variable, i.e., it might be that the number of patients providing data to an analysis is smaller than the number of patients in the FAS.

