12.5.7 Patient Reported Outcomes (PROs)

Patient reported outcomes will be evaluated based on FAS unless otherwise specified.

BASDAI

The following variables will be evaluated:

- BASDAI

For BASDAI, see [Section 12.5.1](#) Efficacy and/or Pharmacodynamic endpoint(s) for details.

[REDACTED]

BASFI

See [Section 12.5.1](#) Efficacy and/or Pharmacodynamic endpoint(s).

[REDACTED]

Patient's assessment of back pain intensity (VAS)

Summary statistics of observed data by visit and change from baseline in patient's assessment of back pain intensity will be provided for each treatment.

SF-36

The following variables will be evaluated:

- SF-36 domain scores (based on a scale of 0-100)
- SF-36 PCS [REDACTED] (norm-based scores)
- SF-36 PCS [REDACTED] (improvement of ≥ 2.5 points, [Lubeck 2004](#))

For the change in SF-36 summary scores (PCS [REDACTED]), summary statistics will be provided using observed data for each treatment regimen.

[figure not shown]
For the responder analyses, the proportion of responders will be descriptively summarized along with its 95% CI for each randomized treatment based on observed data.

The SF-36 domain scores will be summarized by treatment.

ASQoL

[figure not shown]
See [Section 12.5.1](#) Efficacy and/or Pharmacodynamic endpoint(s).

[figure not shown]
[REDACTED]

PSQI

See [Section 12.5.1](#) Efficacy and/or Pharmacodynamic endpoint(s).

The secukinumab i.v. regimen will be compared for primary and secondary variables as part of the regular statistical models (e.g., logistic regression and MMRM).

[figure not shown]
For binary variables, the proportion of responders for these endpoints (e.g., achieving ASAS20) may be summarized along with its 95% CI for each randomized treatment based on observed data. Details will be provided in the statistical analysis plan.

Between-treatment comparisons for binary variables in the FAS population (e.g., ASAS20, ASAS40, ASDAS inactive disease, etc.) at individual analysis visits will be evaluated in a logistic regression model with treatment group, stratification factor (disease condition) as factors and baseline score (if appropriate) and weight as covariates. Difference in marginal

response proportions with p-value and 95% CI will be presented for treatment comparison up to Week 16.

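### The SF-36 PCS responder proportion is summarised on observed data only, so its Week 52 value may be biased upward; an imputed proportion on the full FAS denominator should stand beside it

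*SAP*

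**What the plan says.** - **Observed-data rule.** SAP section 2.11 lists the variable "SF-36 PCS (improvement of ≥ 2.5 points" and then states that "the proportion of responders will be descriptively summarized along with its 95% CI for each randomized treatment based on observed data". The sentence stands under the SF-36 entry and names no visit. This SAP serves the final analysis: sections 2.5 and 2.6 say that the Week 16 primary and secondary analyses are not repeated.
- **Other binary endpoints.** The text after the PRO list in Protocol section 12.5.7 says that proportions such as ASAS20 "may be summarized along with its 95% CI for each randomized treatment based on observed data", with details left to the SAP.
- **Reach of imputation.** Protocol section 12.4.3 introduces its missing-data rule with ASAS40 and "other binary efficacy variables (e.g., ASAS 5/6, etc.) for data up to Week 16 will be handled as follows". What follows is non-responder imputation. No public text extends it past Week 16.
- **Routes to missing data.** Under Protocol section 9.1.1, "the investigator should discontinue study treatment for a given subject if there is a lack of improvement or worsening of their symptoms". Under section 6.2.3, subjects who are judged not to benefit are "free to discontinue participation in the study at any time".
- **Counterweight.** Section 9.1.1 also says that subjects who stop treatment "should NOT be considered withdrawn from the study UNLESS they withdraw their consent", and asks them to attend scheduled assessments where possible. It also asks for the final visit of the period 4 weeks after the last dose.
- **Use of the data.** Protocol section 1.2 says that "to further support efficacy and safety of an i.v. regimen, data will be collected for up to 52 weeks of treatment", and adds that efficacy data may support registration.

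**The concern.** An observed-data proportion divides responders by the subjects who still have a value. If the subjects without a value are mostly failures, the proportion rises although nobody has improved. Its confidence interval is centred on the same shifted value, so it gives no warning. Here the plan itself links poor response to stopping, and allows subjects who do not benefit to leave.

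At stake is how the 52-week results are read. A Week 52 observed-data proportion could be set beside a Week 16 figure in which drop-outs count as non-responders. Part of any apparent gain between the two would then come from the change of denominator.

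**Working it through.** **No plan figure to reproduce.** The documents state no Week 52 response rate and no drop-out after Week 16. The 10% drop-out in Protocol section 5 is for the time before Week 16, and the stated power of about 96% concerns ASAS40 at Week 16.

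**Step 1: who leaves the Week 52 SF-36 denominator?** Protocol Table 8-1 schedules the SF-36 at baseline and Weeks 8, 16, 24 and 52. It is not scheduled at the Week 60 follow-up. SAP Table 5-4 (Group 3) gives the windows Week 16 = days 86–141, Week 24 = days 142–267 and Week 52 = days 268–435. With nominal day = 7 × week + 1, and the final visit 28 days after the last dose:

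| Last dose | Day of last dose | Day of final visit | SF-36 window |
|---|---|---|---|
| Week 16 | 113 | 141 | Week 16 |
| Weeks 20–32 | 141–225 | 169–253 | Week 24 |
| Weeks 36–44 | 253–309 | 281–337 | Week 52 |

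Subjects whose last dose is at Week 36 or later are therefore counted at Week 52 if they attend the final visit. Those whose last dose is at Week 32 or earlier are counted only if they return for later assessments.

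**Step 2: size of the bias.** Let d be the fraction missing at Week 52, p_obs the rate among the observed and p_mis the rate among the missing. The rate in all subjects is (1 − d) × p_obs + d × p_mis, so

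bias = d × (p_obs − p_mis).

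For an assumed p_obs of 55%, in percentage points:

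| d (assumed) | p_mis = 55% | p_mis = 27.5% | p_mis = 0 |
|---|---|---|---|
| 10% | 0 | 0.10 × 27.5 = 2.75 | 0.10 × 55 = 5.5 |
| 25% | 0 | 0.25 × 27.5 = 6.9 | 0.25 × 55 = 13.75 |

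The last column is the gap between the observed and the non-responder-imputed proportion: 55% against 49.5%, and 55% against 41.25%.

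**Step 3: a rate nearer to this endpoint.** Protocol Table 12-2 plans a mean SF-36 PCS change of 6.87 on secukinumab with SD 6.898. If changes are normally distributed, the proportion that improves by at least 2.5 is Φ((6.87 − 2.5)/6.898) = Φ(0.634) = 73.7%. This is a Week 16 planning value and serves only as an illustration. In an arm of 250 with 10% missing (225 observed), and with the SAP's continuity-corrected score interval:

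- observed data: 166/225 = 73.8% (95% CI 67.4 to 79.3)
- non-responder imputation: 166/250 = 66.4% (95% CI 60.1 to 72.2)

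The gap is 7.4 points. The observed estimate lies above the whole imputed interval, and the imputed estimate lies below the whole observed interval.

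**The case against.** The strongest objections are these.

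- **Scope.** A reader might infer that all responder proportions after Week 16 are observed-data only. The documents do not show that. The firm sentence covers one SF-36 variable that is outside the testing sequence. For ASAS and ASDAS endpoints the protocol only permits it. The public SAP passes from section 2.6 to 2.8 and from 2.11 to 2.14, so a rule for them may exist and must not be called absent. Nor is a change of rule at Week 16 established for the SF-36 responder, because Protocol section 12.5.7 gives the observed-data rule without any Week 16 boundary. This objection stands, and it limits the point to the SF-36 responder and, conditionally, to the others.
- **Stopping is not missing.** A reader might also infer that every subject stopped for lack of improvement is lost. Section 9.1.1 keeps them in the study, and the wide Week 52 window recovers late stoppers. This stands in part. Attendance is asked for only where possible, an early final visit is also requested, and earlier stoppers who do not return are still lost.
- **Inflation is not demonstrated.** With no drop-out figure after Week 16, the size rests on assumptions, and the upper ends treat every missing subject as a non-responder. This stands: the rates may be biased upward, but the documents do not show that they are.
- **Importance.** Inference stops at Week 16, later data are descriptive, and the filing analysis is the Week 16 analysis. This stands, and it sets the weight of the point.

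**Conclusion.** The point holds in limited form. The SF-36 PCS responder proportion is tied to observed data, the plan contains outcome-related routes to missing data, and the follow-up provisions offset them only in part. The Week 52 proportion and its interval may therefore be too high. At an assumed observed rate of 55%, the bias is 0 to 5.5 points with 10% missing and 0 to about 14 points with 25% missing. It is zero if missing subjects respond as often as observed ones, and reaches the upper end only if none of them respond. The same reasoning applies to other binary endpoints only if the protocol's permission is used for them without an imputed companion. Primary and secondary inference at Week 16, type I error and power are untouched. It is a cheap improvement to a descriptive output.

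**What to change.** - Beside each observed-data responder proportion after Week 16, present a non-responder-imputed (or multiply imputed) proportion with its 95% CI.
- Use the full FAS by randomised treatment as the denominator. Restricting it to subjects who entered Treatment Period 2 would remove earlier drop-outs, whom the Week 16 rule keeps as non-responders, and would create a new break in the denominator. For the same reason, do not move placebo subjects who never switched into a separate sequence for this table.
- Report the number observed and the number missing at each visit.
- Use one missing-data rule throughout any plot over time.

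If missing subjects respond no better than observed ones, the observed and non-responder-imputed figures bracket the all-subject rate. The cost is one extra set of descriptive outputs, and Week 52 rates that look lower.
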